### **5.8 2 year follow-up**

- QoL and patient satisfaction Questionnaire (Appendix C)
- Post-operative complications (including SAEs)
- Pain assessment measured with VAS score\*

Follow-up at 2 year: All patients will be contacted by phone in order to complete a self-assessment questionnaire.

\*Patients who complain of any trouble will be invited to have a clinical visit at the surgeon's office. Post-operative complications and VAS score will be recorded.

## **6. Statistical Methods**

### **6.1 Sample Size Calculation**

As described in the literature, the worst recurrence rate following incisional hernia repairs using synthetic mesh by laparoscopic and open approach, is 5.9 % [5] and 5.6 % [6] respectively.

Assuming a 95% confidence interval, a recurrence rate of 5.9 % with a +/- 5% precision, N=86 patients are needed for the Evaluable Population. Anticipating a 15% lost to follow up at 24 months, we plan to recruit a *minimum* of 100 patients for this observational registry as the Evaluable Population. Patients that are lost to follow-up or that withdraw consent will not be replaced.

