### **6.2 Statistical Analysis Plan Summary**

#### **General Considerations**

Statistical analysis will consist of descriptive analysis. A statistical analysis plan will be developed by Club Hernie.

- Qualitative variables will be described by their absolute and relative (%) frequencies of each class or value, and by two-tailed 95% confidence intervals.
- Quantitative variables will be described by their mean, standard deviation (SD), extreme values (minimum and maximum values), and number of missing data and by two-tailed 95% confidence intervals.

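### Section 6.1 promises a recurrence rate known to within 5 points either side; with about 5 expected recurrences, a 95% interval with adequate coverage reaches about 7 points above the estimate

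*Protocol*

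**What the plan says.** Protocol section 6.1 takes 5.9% as the worst published recurrence rate after synthetic mesh repair and sizes the registry on it: "Assuming a 95% confidence interval, a recurrence rate of 5.9 % with a +/- 5% precision, N=86 patients are needed for the Evaluable Population". It then allows for attrition ("Anticipating a 15% lost to follow up at 24 months") and sets a minimum recruitment of 100 without replacement, which leaves about 85 patients at two years. Section 6.1 gives no other quantitative reason for the size of the study.

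Section 6.1 does not name the type of interval. Section 6.2 (General Considerations) specifies "two-tailed 95% confidence intervals" for categorical variables, also without naming a method, and leaves the details to a separate analysis plan.

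**The concern.** A margin of 5 points on each side of 5.9% means an interval of 0.9% to 10.9%. That symmetric form comes from the normal approximation to the binomial, which is poor when only a handful of events is expected. If the approximation is off, the protocol claims a precision that its sample size cannot give.

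The study is descriptive and its primary objective is complication incidence, with recurrence named among the complications. The interval around the rate is therefore the result itself, and for a mesh newly marketed in the EU the upper limit carries the safety message. A reader of 6.1 would expect an observed rate near 5.9% to exclude anything above about 11%.

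**Working it through.** **Inputs (Protocol 6.1 and 6.2).** Assumed recurrence rate p = 0.059; half-width d = 0.05; two-sided 95% confidence, z = 1.96; 86 evaluable patients; 15% attrition from 100, so 100 × 0.85 = 85.

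**Step 1: reproduce the protocol's figure.** Normal-approximation formula: n = z² p(1 − p) / d² = 1.96² × 0.059 × 0.941 / 0.05² = 85.3, rounded up to 86. The match is exact, and the half-width at n = 86 is 1.96 × √(0.059 × 0.941 / 86) = 0.0498. The Wald interval as the basis is an inference from this match, since the protocol does not name it.

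**Step 2: expected events.** 86 × 0.059 = 5.07; 85 × 0.059 = 5.02.

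**Step 3: coverage at a true rate of 5.9%, n = 86.** Compute the interval for every possible count and sum the binomial probabilities of the counts whose interval contains 0.059.

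| Interval | Actual coverage |
|---|---|
| Wald | 88.4% |
| Wilson | 96.5% |
| Clopper-Pearson | 98.2% |

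For Wald, the upper limit lies below the truth in 11.1% of samples and the lower limit lies above it in 0.5%. The 11.1% is the chance of seeing 0, 1 or 2 recurrences: at 2/86 the Wald upper limit is 5.5%, already under 5.9%. With n = 85, Wald coverage is 88.0%.

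**Step 4: intervals at the expected count.**

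| Data | Wald | Wilson | Clopper-Pearson |
|---|---|---|---|
| 5/86 (5.8%) | 0.9–10.8% | 2.5–12.9% | 1.9–13.0% |
| 5/85 (5.9%) | 0.9–10.9% | 2.5–13.0% | 1.9–13.2% |

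**Step 5: distance from the estimate at 5/86 (5.81%).**

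- Wilson: 12.90 − 5.81 = 7.1 points above; 5.81 − 2.51 = 3.3 below; mean half-width 5.2.
- Clopper-Pearson: 13.05 − 5.81 = 7.2 points above; 5.81 − 1.91 = 3.9 below; mean half-width 5.6.

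**Step 6: would the full 100 rescue the claim?** With all 100 evaluable and a rate of 5.9%, the upper limit is 12.3% (Wilson) or 12.5% (Clopper-Pearson), which is 6.4 to 6.6 points above the rate. It would not.

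**The case against.** The strongest reply is that nothing has been miscalculated. The normal formula is a common planning approximation, and 86 is what it gives. If precision means average half-width, the miss is modest: 5.2 points for Wilson and 5.6 for Clopper-Pearson, against 5. The lower arm is tighter than promised. The analysis is descriptive with no threshold, so no decision turns on the difference, and 100 is a minimum. All of this stands, and it limits the weight of the point. It does not rescue the claim of 5 points on both sides, because the upper arm is about 7. Even the narrower Jeffreys interval reaches 12.3% at 5/86, which is 6.5 points above the estimate.

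A second reply is that the choice of interval belongs to the analysis plan, which is not at hand. That is right for the reporting method. But if that plan names Wilson or Clopper-Pearson, the margin in 6.1 is still not met at 86 patients.

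A reader might go further and infer that complication rates will be reported with Wald intervals, giving negative lower limits or a zero-width interval when no event is seen. The protocol does not say so: section 6.2 names no method, and sizing by an approximation does not commit the analysis to it. Nor do the documents show that most other complications will be as rare as recurrence. They give no expected rates for them, and the endpoint list in section 6.2 includes pain and all complications combined, which could be common.

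**Conclusion.** The point holds for the precision statement in 6.1 and no further. For about 5 recurrences among 85 or 86 patients, a 95% interval with adequate coverage runs from roughly 2% to 13%, not 0.9% to 10.9%. The shortfall is on the upper side, about 2 points beyond the stated 5. The lower side is better than stated.

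This rests on the protocol's own 5.9% and its sample size, and on the inference that 86 came from the Wald formula. The limits for 5/86 and 5/85 do not depend on that inference.

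A reader might also conclude that the registry is too small. Bringing the upper arm within 5 points at 5.9% would take about 150 (Wilson) or 153 (Clopper-Pearson) evaluable patients, but the protocol sets no requirement for the upper arm alone and tests no threshold. The consequence is overstated precision, not an inadequate trial or a wrong decision rule.

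**What to change.** In section 6.1, replace the symmetric margin with the interval the design delivers, for example: *with about 85 evaluable patients and 5 recurrences (5.9%), the exact 95% confidence interval is 1.9% to 13.2%*. Add that the two-year recurrence rate will be reported with that same method, Clopper-Pearson or Wilson, so that planning and reporting agree. If Wilson is chosen, the corresponding interval is 2.5% to 13.0%.

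The cost is two sentences and a less favourable stated precision. Enrolment, follow-up and data collection do not change.

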## **4. Patient Selection**

The first one hundred consecutive adult patients scheduled for primary and incisional abdominal wall hernia surgery by Club Hernie members surgeons using Symbotex™

Composite Mesh (Flat sheet (SYM), Flat Sheet with sutures (SYM-F), with flap (SYM-OS) by open or laparoscopic approach. Patients' data will be reported in the Club Hernie database in real time.

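### Section 6.1 gives the label Evaluable Population to both 86 and 100 patients, while its own loss assumption leaves 85, so the denominator of the 24-month recurrence rate is open

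*Protocol*

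**What the plan says.** Section 6.1 of the protocol sizes the registry on recurrence: "Assuming a 95% confidence interval, a recurrence rate of 5.9 % with a +/- 5% precision". The result is 86 patients for the Evaluable Population. The next sentence begins "Anticipating a 15% lost to follow up at 24 months" and sets recruitment at a minimum "of 100 patients for this observational registry as the Evaluable Population". The section closes by ruling out replacement of patients who are lost or withdraw. The protocol does not define the Evaluable Population anywhere else.

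Sections 1, 2.2 and 4 give one hundred patients without calling it a minimum. Section 4 takes "The first one hundred consecutive adult patients scheduled for primary and incisional abdominal wall hernia surgery".

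In section 6.2, the analysis summary lists recurrence among the primary endpoints and refers their analysis back to the General Considerations. There, qualitative variables are described "by their absolute and relative (%) frequencies of each class or value, and by two-tailed 95% confidence intervals". No denominator is named for the 24-month rate.

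**The concern.** One label covers two sets that cannot coincide. If 100 patients are recruited, 15% are lost and none is replaced, the 100 cannot all be evaluable at 24 months. The number that remains also differs from the 86 stated one sentence earlier.

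The consequence lies in the analysis. Recurrence at 24 months is the quantity that sized the registry, and the protocol ties it to a crude percentage. With the Evaluable Population attached to two numbers, an analyst could divide by all recruited patients or by those followed up, and find support for either in section 6.1. The two choices give different rates and treat lost patients differently.

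**Working it through.** **Inputs.** From section 6.1: expected recurrence p = 0.059, half-width d = 0.05, 95% confidence, 15% loss at 24 months, no replacement, 100 recruited. From section 6.2: intervals are two-tailed, so z = 1.96.

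**1. The plan's own figure.** Normal-approximation (Wald) precision for one proportion:

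n = z² p(1 − p) / d² = 1.96² × 0.059 × 0.941 / 0.05² = 85.31, rounded up to 86.

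The stated 86 is reproduced.

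**2. Allowance for loss.**
- Evaluable from 100 recruited: 100 × 0.85 = 85.
- Recruitment that keeps 86: 86 / 0.85 = 101.2, so 102.
- The same from the unrounded requirement: 85.31 / 0.85 = 100.4.

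**3. Precision at each candidate number.** Half-width = 1.96 × √(0.059 × 0.941 / n):

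| n | Half-width (points) |
|---|---|
| 85 | 5.01 |
| 86 | 4.98 |
| 100 | 4.62 |

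The step from 86 to 85 costs about 0.03 points. Reading the Evaluable Population as 100 rather than 85 changes the claimed precision by about 0.4 points.

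**4. Effect on the reported rate.** Assume five recurrences are recorded (an illustration; the documents give no count):
- 5/100 = 5.0%, exact 95% CI 1.6 to 11.3%.
- 5/85 = 5.9%, exact 95% CI 1.9 to 13.2%.

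**5. Effect of counting lost patients as recurrence-free.** Assumptions, none from the documents except the 5.9% and the 15%: true 24-month risk 5.9%, half the events by 1 year (2.95 per 100 in each year), losses split evenly (7.5% before the 1-year contact, 7.5% between 1 and 2 years), and loss unrelated to recurrence.
- Recurrences seen per 100 enrolled: 2.95 × 0.925 + 2.95 × 0.85 = 2.73 + 2.51 = 5.24. Over 100 this is about 5.2%, against a true 5.9%.
- Complete cases: 5.9 × 0.85 = 5.015 recurrences in 85 patients, or 5.9%. There is no bias under these assumptions.
- Interval estimate, where a patient enters an interval's risk set only if the contact that closes it was made: year 1 risk 2.73 / 92.5 = 0.0295. Year 2 risk 2.51 / (97.05 × 0.85) = 2.51 / 82.49 = 0.0304. Cumulative risk 1 − 0.9705 × 0.9696 = 5.9%.

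**The case against.** The strongest reply is that this is a wording slip. The order of the sentences (86 needed, 15% loss expected, therefore at least 100) shows that 100 is the inflated recruitment number. The miss is rounding, since the unrounded requirement gives 100.4, and a minimum of 100 permits 102. The summary in section 6.2 announces a separate statistical analysis plan, where analysis sets and the handling of lost patients are commonly settled. It also says that all data will be analysed, which speaks against discarding a recorded 1-year recurrence.

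Much of this stands. The one-patient miss is trivial and is no reason to enlarge the registry. A reader might infer that 118 must be recruited (100 / 0.85 = 117.6), but the run of the sentence does not support taking 100 as the number wanted after loss.

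Two parts do not stand. The word minimum is a weak defence when section 4 takes the first one hundred consecutive patients. And the protocol does more than leave the matter to a later plan: it applies its Evaluable Population label to two different numbers and ties recurrence to a crude percentage. A later analysis plan could cite either number.

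The life-table proposal may be called a preference in a purely descriptive registry. It is still descriptive, and it uses contacts already scheduled.

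**Conclusion.** The inconsistency is real and should be corrected. It is small as a sample-size matter and moderate as a reporting matter. Under the protocol's own figures about 85 patients are evaluable at 24 months, with a half-width of 5.01 points. The open denominator moves an illustrative five recurrences from 5.0% to 5.9%.

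A reader might infer that the 24-month rate is biased downward whichever denominator is used. The documents do not support that. A denominator of 100 understates the risk if any lost patient recurs unseen (about 5.2% for a true 5.9% under the assumptions in step 5). Complete cases are biased only if loss is related to recurrence, and the direction is not known. Patients who recur might be harder to reach. Equally, patients with complaints are invited to a clinic visit (sections 2.2, 5.7 and 5.8), which might keep them in contact.

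The arithmetic on 85, 86 and 100 rests only on section 6.1. The five recurrences, the timing of events and the pattern of loss are assumptions made for illustration.

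**What to change.** **Section 6.1.** Call the 100 enrolled. Define the Evaluable Population once, as patients with known 24-month recurrence status, and say whether a patient whose recurrence was recorded at 1 year and who was then lost counts as known. State about 85 evaluable with a precision of about ±5.0 points. Make the minimum of 100 agree with the one hundred of sections 1, 2.2 and 4. No additional patients are needed.

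**Section 6.2.** Report 12- and 24-month recurrence by a life-table estimate over the scheduled contacts (D30, 1 year, 2 years) in all operated patients, censored at last contact. Give the crude percentage, with its denominator stated, as supportive. This keeps 1-year recurrences in patients who are later lost and does not count lost patients as recurrence-free.

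**Cost.** Wording changes and one extra standard analysis, with no added visit. The contact at which each recurrence was found must be recorded. The estimate assumes non-informative censoring, and event times are known only to the interval between contacts, because the 1- and 2-year questionnaire in Appendix C asks about a new hernia or bulge without a date.

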### **6.2 Statistical Analysis Plan Summary**

#### **General Considerations**

Statistical analysis will consist of descriptive analysis. A statistical analysis plan will be developed by Club Hernie.

- Qualitative variables will be described by their absolute and relative (%) frequencies of each class or value, and by two-tailed 95% confidence intervals.
- Quantitative variables will be described by their mean, standard deviation (SD), extreme values (minimum and maximum values), and number of missing data and by two-tailed 95% confidence intervals.

### **Statistical Analysis Plan Summary**

The analysis will be performed for primary and secondary endpoints, all data will be analyzed, according to the methods previously described in the general considerations section.

- 1) Descriptive Analysis of patients registration and outcomes measurement
- 2) Baseline and Demographic Data Analysis
- 3) Operative Data Analysis
- 4) Primary endpoints measured within 1month, 1 Year and 2 Year follow-up
  - a. Peri-operative complications
  - b. Post-operative complications such as anticipated device related complications as pain, recurrence, complications related to adhesions, wound complications, other postoperative complications, SAEs...
  - c. All complications
- 5) Secondary endpoints analysis during the whole follow-up
  - a. Surgical technique and mesh fixation
  - b. Operative time descriptive analysis
  - c. Ease of use / mesh manipulability assessment by surgeons
  - d. Length of hospital stay analysis
  - e. Quality of life and patient satisfaction analysis
  - f. Surgeon satisfaction

### **Statistical Analysis Schedule**

Interim analyses and one final analysis will be performed on the follow-up data in its entirety.

One final clinical study report will be issued.

## **7 Ethical Considerations, Data storage and Confidentiality**

This study is an observational study; therefore the ISO 14155 Standard is not applicable.

This Observational Registry Study will be conducted according to applicable French regulation. No specific examinations or lab tests are to be performed above and beyond those usually undertaken by the surgeon, and no additional visits are required for study purposes.

The study will be registered on the [www.clinicaltrials.gov](http://www.clinicaltrials.gov) and the study results will be posted on this website.

### **7.1 Patient Information Notice**

A written information notice will be given by the surgeon to inform the patient about the nature of the study.

The physician will provide the patient with the information sheet during the pre-operative visit. This form will contain information concerning the nature and purpose of the Study.

### **7.2 Data Storage and Confidentiality**

Only Hernia Club surgeon members are allowed to get an account for the database, protected by identifier and password.

The database is completed anonymous. Therefore, it does not contain any patient data such as name, date of birth, social security number or address of the patient.

## **8 Safety Assessment**

### **Adverse Event/ Complications**

Symbotex™ Composite mesh is currently marketed within US and this observational registry study will be initiated as soon as marketed in EU. Therefore any device related complications noted in this study will be reported to Covidien.

Study reported device-related events will be reviewed periodically to assess for any potential trends

## **10 Appendix**

10.1 Appendix A: Product description

10.2 Appendix B: Instruction for use

10.3 Appendix C: Quality of Life and patient satisfaction Questionnaire

## Appendix A

### Product description

The proposed Symbotex™ Composite Mesh configurations are summarized in the table below:

	Proposed Symbotex™ Composite Mesh		
	Flat sheet (SYM)	Flat Sheet with sutures (SYM-F)	With flap (SYM-OS)
Photos			
Description	
Symbotex™ composite mesh is made out of a three-dimensional monofilament polyester textile, which is covered with an absorbable, continuous and hydrophilic film on one of its sides. This film is made up of collagen from porcine origin and glycerol. The collagen film is essentially degraded in less than 1 month.
 
A dyed monofilament polyester (D&C Green No. 6) marking is positioned on the center of the textile, on the opposite side of the film, and helps center and orient the mesh.
	
Symbotex™ composite mesh is made out of a three-dimensional monofilament polyester textile, which is covered with an absorbable, continuous and hydrophilic film on one of its sides. This film is made up of a mix of collagen from porcine origin and glycerol. The collagen film is essentially degraded in less than 1 month.
 
Non-absorbable pre-placed sutures are tied to the three-dimensional mesh.
 
A dyed monofilament polyester (D&C Green No. 6) marking is positioned on the center of the textile, on the opposite side of the film, and helps center and orient the mesh.
	
Symbotex™ composite mesh is made out of a three-dimensional monofilament polyester textile, which is covered with an absorbable, continuous and hydrophilic film on one of its sides. This film is made up of collagen from porcine origin and glycerol. The collagen film is essentially degraded in less than 1 month.
 
A dyed (D&C Green No. 6) bi-dimensional monofilament polyester textile flap is attached to the three-dimensional reinforcement and helps place and fix the mesh.

Shape, Reorder and Sizes	
Rectangular: SYM1510 (15x10cm) SYM2015 (20x15cm) SYM2520 (25x20cm) SYM3020 (30x20cm) SYM3728 (37x28cm) SYM4232 (42x32cm)
 
Elliptical : SYM1710E (17x10cm) SYM2012E (20x12cm) SYM2515E (25x15cm) SYM3420E (34x20cm) SYM4024E (40x24cm)
 
Circular : SYM9 (9cm diameter) SYM12 (12cm diameter) SYM15 (15cm diameter)
	
Rectangular: SYM1510F (15x10cm) SYM2015F (20x15cm) SYM2520F (25x20cm) SYM3020F (30x20cm) SYM3728F (37x28cm) SYM4232F (42x32cm)
 
Elliptical : SYM1710EF (17x10cm) SYM2012EF (20x12cm) SYM2515EF (25x15cm) SYM3420EF (34x20cm) SYM4024EF (40x24cm)
 
Circular : SYM9F (9cm diameter) SYM12F (12cm diameter) SYM15F (15cm diameter)
	
Circular : SYM8OS (8cm)
 
Rectangular: SYM1510OS (15x10cm) SYM2015OS (20x15cm) SYM2520OS (25x20cm) SYM3020OS (30x20cm)

## **APPENDIX B**

### **Instruction for Use**

[figure not shown]

# Symbotex™

## Composite Mesh

1074068

EN

### BEFORE USING PRODUCT, READ THE FOLLOWING INFORMATION THOROUGHLY.

#### IMPORTANT!

This booklet is designed to assist in using this product. It is not a reference to surgical techniques. This device was designed, tested and manufactured for single patient use only. Reuse or reprocessing of this device may lead to its failure and subsequent patient injury. Reprocessing and/or resterilization of this device may create the risk of contamination and patient infection. Do not reuse, reprocess or resterilize this device.

#### DESCRIPTION

Symbotex™ composite mesh is made out of a three-dimensional monofilament polyester textile, which is covered with an absorbable, continuous and hydrophilic film on one of its sides. This film is made up of a mix of collagen from porcine origin and glycerol. The collagen film is essentially degraded in less than 1 month.

A dyed (D&C Green No. 6) bi-dimensional monofilament polyester textile flap is attached to the three-dimensional reinforcement and helps place and fix the mesh.

#### INDICATIONS

Symbotex™ composite mesh is intended for the reinforcement of abdominal wall soft tissue where a weakness exists, in procedures involving primary abdominal wall and incisional hernia surgeries.

The non-absorbable three-dimensional polyester mesh provides long term reinforcement of soft tissues. On the opposite side, the absorbable hydrophilic film minimizes tissue attachment to the mesh in case of direct contact with the viscera.

#### CONTRAINDICATIONS

- As Symbotex™ composite mesh will not stretch to accommodate growth, its use is not appropriate in patients in a period of growth.
- Any foreign material may potentiate or prolong infection in the presence of bacterial contamination, and as such, the use of Symbotex™ composite mesh is not appropriate in an infected or contaminated site. Furthermore, this product should be used with the understanding that infection may require removal of the device.

